3.3 Study duration: March 2026 – March 2030

3.4 Sample Size and Calculation Basis

Based on research reports, the diagnostic accuracy of colposcopy for low-grade lesions is only approximately 43.4%, while the diagnostic accuracy for high-grade lesions ranges from 59% to 76%. A domestic multicenter study demonstrated that traditional colposcopy has a specificity of 75.1% and a sensitivity of 70.2% in detecting high-grade cervical lesions. Control group indicators (P0): According to data, traditional colposcopy achieves a diagnostic accuracy of approximately 59-76% for high-grade lesions (HSIL+). The lower limit of 59% is adopted as the calculation benchmark. Experimental group expected indicators (P1): It is hypothesized that high-definition magnified electronic colposcopy can significantly improve detection rates. A 20-percentage-point improvement is required to achieve statistically significant clinical significance, with diagnostic accuracy potentially reaching around 79%. Prevalence in target population: Literature reports indicate that among participants undergoing colposcopy, the proportion of cases ultimately pathologically confirmed as high-grade lesions (HSIL+) ranges from 20% to 40%, with a set threshold of 30%. Statistical power (Power, $1-\beta$): Set at 90%, with $\alpha = 0.05$ (two-tailed).

Methods: Sample size estimation was performed using the sample size calculation formula for paired design diagnostic tests (McNemar test). A minimum of 212 study participants with complete paired data and valid gold standard results were required, accounting for a dropout rate of 10%-20%. The final planned total sample size was 270 cases.

Continuous enrollment was employed to include all eligible participants who met the inclusion criteria and consented to participate in the study until the target sample size was achieved. To balance potential biases arising from examination

sequence, a simple randomization method was used to assign participants to two distinct examination sequences (Sequence A group: initial observation and image acquisition using a conventional optical colposcope (magnification 7.5-15x), followed by endoscopy (preset magnification 90-120x); Sequence B group: initial examination using an endoscope, followed by colposcopy).

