3.6 Methods and Procedures

The same study participant was randomly assigned to groups A and B according to sequence randomization, with examination sequences conducted in two groups.

Procedure for Evaluation Method 1 (Colposcopy): Study participants were placed in the lithotomy position. After routine disinfection and draping, a speculum was inserted. Traditional colposcopy was performed at designated time points (after saline administration, 1 minute and 2 minutes post-acetic acid test, and post-iodine test). The colposcopy specialist interpreted imaging features, recorded proposed diagnostic opinions, and marked suspected lesion sites (denoted as Point Y). The cervical surface was conceptualized as a clock face centered on the cervical os, with

the 12 o'clock position representing the top of the cervix. For example, Y6 indicates suspected cervical lesion at the 6 o'clock position under colposcopy.

[figure not shown]
Evaluation of Probe Method 2 (High-Definition Electronic Magnification Endoscopy + Image Enhancement Technology): Procedure Flow: In the same study participants, high-definition electronic magnification endoscopy combined with image enhancement technology was used to observe the cervix and vagina and acquire images at specified time points (after saline administration, 1 minute after acetic acid test, 2 minutes after acetic acid test, and after iodine test). The endoscopist interpreted the images based on characteristic features, recorded proposed diagnostic opinions, and marked suspicious lesion sites on the schematic diagram (denoted as N-point, e.g., N3 indicates suspected cervical lesion at point 3 under endoscopic evaluation; lesions simultaneously identified as suspicious by colposcopy and endoscopy are labeled as T-point, e.g., T9 indicates suspected cervical lesion at point 9 according to both examinations).

Biopsy specimens from suspicious sites (2-4 mm per tissue block, totaling 2-4 tissue blocks) were submitted for examination. Endoscopists and colposcopists were unaware of each other's interpretation results. Pathologists conducted microscopic examination of the biopsy specimens and issued pathological diagnosis results (pathologists were unaware of the grouping and proposed microscopic diagnosis results).

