For study participants who showed no suspicious lesions on conventional colposcopy or endoscopy, informed consent was obtained to voluntarily opt for biopsy. Those who chose biopsy had their pathological results compared with the proposed microscopic diagnosis using the gold standard. Participants opting against biopsy underwent 6-12 month follow-up HPV and TCT testing. Those with negative follow-up HPV/TCT results, abnormal HPV/TCT findings, or persistent negative results after colposcopy evaluation or colposcopic biopsy pathology were classified

as true negatives (suboptimal microscopic diagnosis negative with follow-up gold standard confirmation). Participants with \geq CINII or VAINII findings after 6-12 month colposcopic biopsy were categorized as false negatives (no suspicious lesions detected microscopically but confirmed high-grade lesions by follow-up gold standard). Image feature analysis was performed between experimental and control groups, with accuracy validated through pathological or follow-up results. Adverse events were recorded 24 hours post-examination (when vaginal swabs were removed after biopsy) for participants undergoing both instrument-based examinations.

technology roadmap :

3.7 Evaluation indicators:

Primary outcome measure: accuracy rates of the two examinations, with histopathological results or follow-up outcomes serving as the gold standard.

Secondary outcome indicators: sensitivity, specificity, positive predictive value, negative predictive value, AUC, and lesion recognition rate (referring to the ability to identify suspicious lesions through high-definition magnified endoscopy in cases that are difficult to detect with conventional colposcopy).

Efficacy indicators: clarity of lesion margins and visualization capability of microvascular structures (including resolution of point-like, clustered, and spiral patterns), assessed using a 4-point Likert scale: 1=poor, 2=average, 3=good, 4=excellent.

Safety indicators: Examination-related adverse event incidence rate (e.g., bleeding, infection, mucosal injury or perforation during the procedure), postoperative complication rate within 24 hours (e.g., lower abdominal discomfort, vaginal bleeding, fever), and examination tolerance (assessing the proportion of study participants who discontinued the examination midway or requested termination of the procedure).

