Study participants may opt out of this research without any adverse impact on their access to conventional treatments. For this condition, standard therapeutic approaches include: performing only traditional colposcopy, with biopsy taken when necessary based on endoscopic findings to guide subsequent management plans. If

biopsy is not required, regular follow-up examinations are recommended. Traditional colposcopy has a long history and is performed by highly skilled practitioners, but its imaging quality is suboptimal, resulting in poor visualization of the cervical canal.

This may lead to unnecessary biopsies and endocervical curettage (ECC).

5、 Data Management and Information Confidentiality

During the study period, personal information such as the names and genders of study participants will be replaced with codes or numbers and strictly confidential. Only the relevant physicians will be aware of their data, ensuring robust protection of participants' privacy rights. Study findings may be published in academic journals, but no personal information of study participants will be disclosed.

If study participants consent to participate in this study, all their medical records will be reviewed by relevant personnel from the research institution initiating this study and relevant authoritative agencies, or by an independent ethics committee, to assess the appropriateness of study procedures.

6、 Adverse Event Management

Study participants required the insertion of specula and application of acetic acid or iodine tincture to the cervical and vaginal mucosa. Biopsy may be necessary when indicated. Mild pain, mucosal trauma, or slight vaginal bleeding are considered normal phenomena. If major vaginal bleeding, allergic reactions, or infections occur during or within 24 hours post-procedure (before follow-up completion) and cannot be ruled out as unrelated to the procedure, they shall be classified as adverse events. The procedure must be immediately discontinued, and the research team will provide prompt medical intervention to participants while reporting the incident within 24 hours.

VII. Ethical Principles and Requirements for Life Sciences and Medical Research

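### Adverse event collection closes at 24 hours with no later safety query for biopsied women, so biopsy-related infection or bleeding that begins later counts as zero

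*Protocol*

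**What the plan says.** Protocol 3.7 (Evaluation indicators) lists two event rates among the safety indicators. The first is "Examination-related adverse event incidence rate (e.g., bleeding, infection, mucosal injury or perforation during the procedure"; the second is "postoperative complication rate within 24 hours (e.g., lower abdominal discomfort, vaginal bleeding, fever".

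Protocol 3.6 (Methods and Procedures) fixes the recording time: "Adverse events were recorded 24 hours post-examination (when vaginal swabs were removed after biopsy".

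Protocol section 6 (Adverse Event Management) first sets aside minor effects: "Mild pain, mucosal trauma, or slight vaginal bleeding are considered normal phenomena". It then defines what counts: "If major vaginal bleeding, allergic reactions, or infections occur during or within 24 hours post-procedure (before follow-up completion", provided a link to the procedure cannot be excluded. The duty to report is attached to that definition.

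On exposure, 3.6 states: "Biopsy specimens from suspicious sites (2-4 mm per tissue block, totaling 2-4 tissue blocks) were submitted for examination". The only later study contact described is for women in whom neither examination showed a suspicious lesion and who declined biopsy: "Participants opting against biopsy underwent 6-12 month follow-up HPV and TCT testing". That testing supplies their reference standard, and no safety question is attached to it.

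**The concern.** The biopsy is the step that breaks tissue, and its infectious and delayed bleeding complications need not appear on the first day. Recording also ends at the moment the swab comes out, so bleeding that starts once the woman has left falls outside the record.

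Some of the biopsy exposure may come from the study itself. Sites suspected only on endoscopy can add biopsies, and women with no suspicious lesion are offered one. Section 10 of the text on alternatives (heading 4) describes usual care as biopsy when needed and criticises colposcopy for leading to unnecessary biopsies, so biopsy harm bears on the trial's own argument.

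At stake is the meaning of the infection and bleeding rates. Protocol 3.8 plans an incidence for each type of event. A low infection rate could be read as evidence of safety when the window could not have captured later infections. Under the section 6 wording, a day-4 infection would also not meet the definition to which reporting is tied.

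**Working it through.** **1. Where the window closes.** There is no calculated figure in the plan to reproduce, so the statements are set side by side.

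| Place | What is covered | Time limit |
|---|---|---|
| 3.6 | Recording of adverse events | 24 hours, at swab removal |
| 3.7, first rate | Bleeding, infection, mucosal injury, perforation | A procedural limit is worded at the end of the list |
| 3.7, second rate | Discomfort, vaginal bleeding, fever | 24 hours |
| Section 6 | Major bleeding, allergic reaction, infection | During the procedure or up to 24 hours |

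The statements agree on 24 hours. The bracketed remark about follow-up completion in section 6 does not set a longer limit, because the sentence itself states 24 hours.

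**2. What follows without any outside figure.** Reported incidence = events with onset up to 24 hours / women examined. An infection or major bleed with later onset contributes 0 to the numerator. This follows from the definition alone.

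**3. How much might be missed.** This is an illustration on assumptions, not an estimate from the documents.

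- From the protocol: N = 270 (3.4: "The final planned total sample size was 270 cases"). Using all 270 overstates exposure, since some women will not be biopsied.
- Assumed: true infection risk r = 0.5% to 2%.
- Assumed: exponential onset time with median m = 2, 3, 5 or 7 days.

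Share with onset within 24 hours: f = 1 − 2^(−1/m).

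- m = 2: f = 29%
- m = 3: f = 21%
- m = 5: f = 13%
- m = 7: f = 9%

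The share missed is 1 − f, from 71% (m = 2) to 91% (m = 7).

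True events = 270 × r, so 270 × 0.005 = 1.35 to 270 × 0.02 = 5.4. Recorded events = 270 × r × f. Chance of recording none = (1 − r × f)^270.

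| Median onset | Recorded at r = 0.5% | Recorded at r = 2% | Chance of none, r = 0.5% | Chance of none, r = 2% |
|---|---|---|---|---|
| 2 days | 0.40 | 1.58 | 67% | 20% |
| 7 days | 0.13 | 0.51 | 88% | 60% |

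**4. What a zero would mean.** With 0 events in 270, the one-sided 95% upper bound is 1 − 0.05^(1/270) = 1.1%. That bound applies to the 24-hour risk only and says nothing about later onset.

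**The case against.** The strongest reply is that the protocol does not hide the window. The complication rate in 3.7 is openly labelled as a 24-hour rate, and the protocol nowhere claims a rate over the healing period. This stands: the passages do not contradict each other. The weakness is that infection and fever are measured through a window that cannot represent their full biopsy-related incidence.

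A reader might also infer several stronger points that the documents do not support.

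- **That infection and bleeding rates will be near zero by construction.** This is established only for events that begin after 24 hours. Bleeding within 24 hours is captured, some infections may be, and a low count would partly reflect rarity.
- **That a given share of events, such as at least 80%, will be missed.** Any such figure restates an assumption about onset timing. A 2-day median, for example, gives 71%.
- **That biopsied women have no later contact.** Heading 4 describes biopsy as guiding later management, which implies clinical contact. The text between 3.1 and 3.3 and the roadmap figure could not be read. What can be said is that no later safety query is described. Protocol 3.8 lists follow-up records and adverse event profiles among the eCRF contents without a time limit, but it creates no such query.
- **That infection is counted only while the procedure is under way.** In 3.7 that qualifier closes a list and may belong only to injury or perforation. Section 6 counts infection up to 24 hours.
- **That follow-up is arranged the wrong way round.** The 6-12 month testing exists to settle disease status in unbiopsied women and was never safety follow-up.

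Two further points stand. Every woman has both examinations, so a delayed biopsy infection can seldom be attributed to one instrument. And 3.5 has an exit criterion for serious adverse events without a 24-hour limit, but it governs exit and does not extend the counting window.

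**Conclusion.** The point holds as a limited weakness in safety measurement. Infection, fever and bleeding are named outcomes, collection and the section 6 definition stop at 24 hours, and no later safety query is described for women giving 2-4 tissue blocks. Infection or bleeding with later onset therefore contributes exactly zero to the reported incidence.

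The number missed is unknown. The 71% to 91% range rests on an assumed exponential onset with median 2 to 7 days. The 1.35 to 5.4 true events rest on an assumed risk of 0.5% to 2% in all 270 women. At such counts the rate would be imprecise under any window. The primary comparison of accuracy is unaffected. This is a worthwhile, inexpensive improvement and not a threat to the trial's main conclusion.

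**What to change.** - Keep the 24-hour record for acute events.
- Add a brief eCRF safety query when the biopsied woman receives her pathology result: bleeding needing care, fever, infection, antibiotic use, unplanned visit, and days since biopsy. Asking about bleeding that needed care keeps the slight bleeding that section 6 treats as normal out of the count.
- For counting and reporting only, extend the section 6 window for infection and bleeding to that query. Leave its discontinuation and treatment wording unchanged.
- State in 3.7 that infection is counted post-procedure, and report 24-hour and later rates separately.
- If the later query is not adopted, limit safety conclusions to events within 24 hours.

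The cost is a few eCRF items and some protocol wording. The query relies on a result-disclosure contact that the protocol does not describe, so that contact would have to be written in. The complication rate may look less favourable.
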